APPENDIX

1. Amendments to the Protocol	12
2. Amendments to the Statistical Analysis Plan	13

PROTOCOL Version 1.3 (See Table of Amendments)

Multi-Center Randomized Controlled Trial of Refeeding in Anorexia Nervosa

1. Introduction

Current recommendations to guide the clinical care of AN patients hospitalized with medical instability due to malnutrition are based solely on retrospective or observational studies and/or clinical experience. No studies to date have prospectively tested high calorie refeeding (HCR) and the long-term impact on recovery is unknown. Consensus has developed over recent decades that patient safety can only be guaranteed using low calorie refeeding (LCR). The entrenchment of clinical practice without supporting evidence is a widely recognized dilemma in healthcare. While RCTs are considered the “gold standard” to establish evidence-based medicine, until recently there was insufficient data to propose such a study of refeeding in AN. We now have preliminary findings to indicate that LCR might be too cautious and that HCR appears feasible and may improve long-term recovery. Thus, we are poised to compare these two treatments in a parallel, randomized fashion.

2. Study Design

The purpose of this multi-center randomized controlled trial is to compare LCR vs. HCR refeeding strategies for hospitalized adolescents with AN. Participants will be recruited upon hospital admission at two centers (UCSF and Stanford) to maximize sample size, and randomly assigned 1:1 within site to one of the two strategies. A total of 120 participants age 12-24 yrs who meet DSM-5 diagnostic criteria for AN and atypical AN and present as medically unstable due to malnutrition will be enrolled. Treatments will not be blinded, since both the patients and clinicians who work with this population are highly skilled at estimating kcal and would be able to determine their group assignment by simply viewing the meal trays. In addition, target kcal will be reached faster in HCR and this would be apparent on physician orders. The proposed study is powered to detect a meaningful difference in clinical remission (Aim 1A).

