2.1. Study Population

- a. **Inclusion/Exclusion:** Adolescents hospitalized for medical instability secondary to malnutrition will be eligible as follows. **Inclusion criteria:** diagnosis of AN, atypical AN, age 12-24 years, no hospital admissions for the previous six months, and meet hospitalization criteria (daytime HR < 50 bpm or night time HR < 45 bpm, BP <90/45 mmHg, temperature < 35.6° C or orthostasis defined by increase in HR > 35 bpm or decrease in systolic BP > 20 mmHg from lying to standing). **Exclusion criteria:** diagnosis of bulimia nervosa [DSM-5], currently in remission (as defined by weight and EDE-Q score per Aim 1), admission for food refusal without malnutrition, current pregnancy, chronic disease (e.g. immune/endocrine disorders, pulmonary, cardiac, or renal disease), current suicidality or psychosis.
- b. **Participant recruitment and consent:** Participants and their parents will sign assent (for those < 18 yr) and consent, respectively within 24 hr of hospitalization. This may occur in the clinic when they are deemed medically unstable and waiting transfer to the hospital or in the hospital if admitted directly. Consent will include permission to review all medical records, to review hospital billing data, and to contact for future research projects. If a participant turns 18 yr while enrolled, s/he will be reconsented. Participants 18 years of age and older are able to consent themselves; thus we will request verbal consent from their parents to complete parent surveys.

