3.2. Data Collection

Other than the treatment we are testing (HCR vs. LCR), patients will receive SOC in the hospital. Thus, as shown in **Table 1**, the vast majority of procedures in hospital are SOC. Follow-up visits, on the other hand, are for the purpose of collecting data and will be scheduled at the designated time points.

- a. **Baseline data collection:** The following covariates will be collected upon admission, prior to randomization.
 - (1) Demographics and eating disorder history: an intake form will be self-administered (with study coordinator as proctor, 15 min) to assess: highest body weight, lowest body, date of onset (to calculate length of illness and rapidity of weight loss), family history of eating disorder, self-reported race/ethnicity, maternal education and zipcode (to indicate socioeconomic status), date of birth.
 - (2) Eating Disorder Examination-Questionnaire (EDE-Q): is a standardized research interview that measures eating disorders psychopathology. [name] (co-I, UCSF) has used this tool extensively in RCTs examining psychotherapeutic modalities and long-term recovery in AN and BN and to categorize lower and higher risk study participants. He will oversee the psychological aspects of this study, including the EDE-Q.
 - (3) Food recall: dietary intake for the day prior to hospital admission will be assessed with a 24-hr food recall by the Research RD and analyzed via Nutrition Data System for Research (NDS-R) for total kcal and macronutrient profile. Dietary Density (DDS) and Variety Scores (DVS) will be calculated since acceptance of more energy dense and variety of foods in hospital has been shown to predict recovery at 8 mo.
 - (4) Severity of illness: %mBMI and HR on admission
 - (5) Health Care Utilization and Missed School (HCUMS) Survey: This proctored interview draws from established tools to assess cost, and has been tailored for AN and integrated with the follow-up form (above). In addition to "other care", it assesses health care utilization in the 6 months prior to admission including medications, physician visits, dental visits, ER visits and laboratory testing. It will be administered by trained research staff, who will document parent- and participant-reported care, supplemented with dates, doses, and other details available in the medical record.

b. Data collection daily in Hospital:

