2.1. Pool of participants

a. Projected pool of eligible participants and accrual rate: At Stanford, in 2012 there were 295 admissions to the dedicated inpatient eating disorders unit, with approximately 36% of patients meeting DSM-4 criteria for AN; 100 similar patients were admitted at UCSF. With the broader eligibility criteria also including DSM-5, we anticipate at least 40% of patients (120 per yr at Stanford and 40 at UCSF) will be eligible. Of those who are eligible, we estimate that at least 50% will agree to participate and thus we will not attempt to achieve equal enrollment across sites. We will accrue 3-4 participants per mo over 3 yr until N=120 is reached and retain 85% of this sample through 12 mo as shown in open follow-up studies of participants with AN.

b. Commitments of Site PIs, Research Teams, and Participants: Both site PIs have successfully recruited and retained AN participants in research projects and seen them to completion and publication. Furthermore, co-I [name] is a faculty biostatistician with extensive experience in clinical trials. She will lead the DCC, aiming to ensure the trial is designed, executed, and analyzed without bias. Patient incentives to participate will emphasize the value of their contributions to medical research and remuneration for their time.

c. Data Analyses:

Sample Description: The study sample will be summarized and described (e.g., mean \pm SD) by stratification factor and baseline covariates to confirm general balance by arm and data will be summarized for completeness of follow-up (e.g., length of stay, last visit).

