2.2. Outcomes

The primary analysis of the study adopts a modified intent-to-treat (mITT) approach to compare outcomes between randomized HCR and LCR participants who received treatment for at least one day. Patients who are ineligible post randomization, provide no assent after parent's consent, or withdraw before receiving any treatment, will not be included in the mITT analysis for reasons of data unavailability, ethics and clinical relevance. Sensitivity analyses will be conducted to check that 1) withdrawal patients are not different from patients in both groups included in mITT in baseline covariates; and 2) including withdrawal patients in the analyses will not change results and conclusion of mITT analyses. The sensitivity analyses will provide us

reassurance of mITT results.

Aim 1A: Primary (long-term) efficacy outcome. A (generalized) linear mixed-effects regression model (GLMM) will compare study arms with respect to achievement and maintenance of clinical remission. Clinical remission is defined as the combination of mBMI and EDE-Q score at mo 1,3,6,12 (separate analyses below) and measured at 1, 3, 6, and 12 months as 1) clinically remitted (yes or no) and 2) weight recovered (percent of mBMI). The models will include time, treatment group, time*treatment group interaction, and unbalanced baseline covariates if any as fixed effects, while sites and patients will be included as random effects to account for the correlation due to clustering. The time*treatment group interaction provides mITT effect of HCR compared to LCR on clinical remission over time. The average remission rates and scores and their 95% confidence intervals (CIs) will be estimated from the model. GLMM accounts for the fluctuating nature of mBMI and EDE-Q in AN and uses all available data with missing at random assumption, instead of a stronger assumption of missing completely at random required in other models. Aim 1 models will be supplemented with secondary analyses: (i) potential moderators at baseline (included in regression models as main effects and interactions with period and time), may include DSM-5 criteria and EDE-Q thresholds of risk and (ii) potential mediators at follow-up (included as time-dependent covariates), may include food recall (DDS and DVS), healthcare utilization, or incidence of AEs. In addition, separate mixed-effects models will analyze continuous versions of mBMI and EDE-Q to describe longitudinal trajectories.

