2.3. Power and Sample-size Considerations

Aim 1. Based on studies of AN remission, **Table 2.A** shows that with $N=60$ per arm we have 80% power on 2-sided 0.05-level test to detect a 20% difference (8% vs. 28%) if data were cross-sectional ($\rho=1$). Our longitudinal data will allow detection of smaller effects, especially if the correlation among outcomes is low ($\rho < 0.8$). We anticipate 85% retention and non-differential dropout by arm. Since **time to medical stability** is also expected to differ by at least 12% (**Table 2.B.**), we will be adequately powered for Aim 1B.

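### Aim 1A adjusts for baseline %mBMI and EDE-Q only if they look unbalanced, with no cut-off; prespecifying both is a cheap change with a modest gain

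*Combined protocol and SAP*

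**What the plan says.** SAP 2.2 (Aim 1A) plans mixed models for remission and for %mBMI at months 1, 3, 6 and 12. Fixed effects are time, arm, their interaction and "unbalanced baseline covariates if any as fixed effects"; site and patient are random. It then states: "The time*treatment group interaction provides mITT effect of HCR compared to LCR on clinical remission over time". It also plans that "The average remission rates and scores and their 95% confidence intervals (CIs) will be estimated from the model".

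The only description of how balance is judged is in SAP 2.1.c, where the sample is summarised "by stratification factor and baseline covariates to confirm general balance by arm". No test or threshold is given. Aim 1B uses a similar imbalance trigger for its Cox model, also without a cut-off.

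Protocol 3.2.a says "The following covariates will be collected upon admission, prior to randomization", and its list includes EDE-Q and %mBMI. It lists what is collected, not what is adjusted for. Protocol section 2 says "Treatments will not be blinded".

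Other uses of baseline data are secondary: possible moderators in SAP 2.2, and in SAP 2.5 an adjustment for unnamed covariates related to loss to follow-up. SAP 2.5 also describes the primary models as using outcomes that start at randomization, whereas SAP 2.2 starts at month 1.

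**The concern.** Remission is built from %mBMI and EDE-Q, so their baseline values are the obvious prognostic covariates. Baseline remission status cannot stand in for them: Protocol 2.1.a excludes anyone "currently in remission (as defined by weight and EDE-Q score per Aim 1"), so its value is the same for every patient.

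In a randomized trial, baseline imbalance is chance. A rule that adjusts only when imbalance is seen therefore gives up most of the precision available from a prognostic covariate, and lets an unstated cut-off decide the primary model after by-arm data can be inspected. Appendix Table 2 (Amendment 1) records that the randomization code was broken for the in-hospital analysis in 2019, so by-arm baseline data could be known before the 12-month model is settled. The documents do not show that this influenced any choice.

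At stake are precision and prespecification. Validity is not: the unadjusted comparison is unbiased on average, and no stated power or sample size changes.

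**Working it through.** **Inputs from the documents.** 60 per arm, two-sided 0.05, 80% power "to detect a 20% difference (8% vs. 28"%) (SAP 2.3); 16% vs 34% at within-patient correlation 0.6 (Table 2.A); 85% retention, so 0.85 × 60 = 51 per arm.

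**Assumptions.** r, the correlation of each measure with its own baseline, is 0.3, 0.5 or 0.7. Unbalanced means a difference above 0.1 SD, above 0.2 SD, or p<0.05.

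**The plan's own figures.** For 8% vs 28%, the pooled normal approximation has null SE √(2×0.18×0.82/60) = 0.0701 and alternative SE √((0.08×0.92+0.28×0.72)/60) = 0.0677. Then (0.20 − 1.96×0.0701)/0.0677 = 0.92, giving 82.2%. The table uses even percentages only (26% would give 75.3%), so this agrees with the stated 80% up to rounding. For 16% vs 34%, effective n per arm is 60×5/(1+4×0.6) = 88.2, giving 79.4%.

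**How often the trigger fires by chance.** The SE of a standardised difference is √(2/60) = 0.183. For 0.2 SD, z = 1.10 and P = 27%; for 0.1 SD, z = 0.55 and P = 58%; for p<0.05, P = 5%. The unstated cut-off largely decides whether a covariate enters.

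**Continuous %mBMI, one visit.** Adjustment multiplies the variance by 1−r², so power is Φ(2.80/√(1−r²) − 1.96): 83.6%, 89.9% and 97.5% at r = 0.3, 0.5 and 0.7, from 80% unadjusted. Simulated power (%), 60 per arm, effect 0.516 SD, 40,000 runs:

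| r | never | p<0.05 | 0.2 SD | 0.1 SD | always |
|---|---|---|---|---|---|
| 0.3 | 80.1 | 80.5 | 81.5 | 82.4 | 83.5 |
| 0.5 | 80.1 | 81.2 | 84.2 | 86.8 | 89.6 |
| 0.7 | 80.0 | 82.0 | 87.7 | 92.9 | 97.4 |

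**Remission, planned random-intercept logistic model.** 16% vs 34% at each of the four months, 60 per arm, 15% random monotone dropout, binary within-patient correlation 0.56, no site effect, 2,000 runs. Power (%) for the arm contrast averaged over months:

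| r | never | p<0.05 | 0.2 SD | 0.1 SD | always |
|---|---|---|---|---|---|
| 0.3 | 81.0 | 80.8 | 81.1 | 81.7 | 82.4 |
| 0.5 | 80.8 | 81.2 | 82.9 | 84.8 | 86.9 |
| 0.7 | 81.2 | 83.0 | 87.1 | 91.7 | 95.0 |

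The paired Monte Carlo SE of always minus the p<0.05 trigger is 0.6 to 0.8 point, so the r = 0.3 gains are barely distinguishable from noise. This longitudinal simulation has not been independently repeated.

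**Remission at a single visit, 8% vs 28%.** Always minus triggered, in points of power (8,000 runs, Wald test), for 0.1 SD / 0.2 SD / p<0.05:

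| r | 60 per arm | 51 per arm |
|---|---|---|
| 0.3 | 0.6 / 0.8 / 1.1 | 0.6 / 1.2 / 1.3 |
| 0.5 | 0.9 / 2.0 / 3.3 | 1.8 / 3.1 / 4.5 |
| 0.7 | 2.4 / 4.6 / 7.5 | 2.8 / 5.6 / 8.8 |

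**Type I error.** Continuous outcome: 5.0–5.1% always adjusted, 2.7–4.7% triggered. Longitudinal remission, 25% in both arms, r = 0.7: 5.2% always, 3.8–4.6% triggered. The trigger is slightly conservative.

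**Time-by-arm interaction.** In a linear model with complete data, a covariate with a constant effect over time cancels from within-patient contrasts, so there is no gain. In the logistic simulation the interaction rejects in 3.0–3.6% of trials under every rule. Because the arm difference there is constant over time, the interaction null is essentially true. The figure shows that this test does not see a sustained difference; it says nothing about power against a growing one.

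**If baseline %mBMI is a modelled outcome (SAP 2.5).** With one common baseline mean for both arms, nothing is left to gain for continuous %mBMI. With separate means and change from baseline as the effect, adjustment multiplies the variance by (1−r²)/(2(1−r)) = (1+r)/2 = 0.65, 0.75 or 0.85. Neither reading helps remission.

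**The case against.** The strongest reply is that nothing is broken. There is no bias, no inflated error and no wrong sample size, so this is an efficiency preference. The gain also misses the interaction that SAP 2.2 calls the effect, so it appears only if a different contrast is made the main one. That is correct and limits the point. However, SAP 2.2 also plans average remission rates from the model, and Table 2.A is powered on a difference in rates, so an arm contrast is already within the plan's intent.

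The size does rest on assumed r. A constant r is favourable: for a four-visit average with within-patient correlation 0.8, the variance is (1+3×0.8)/4 = 0.85. Then r = 0.5 throughout explains 0.25/0.85 = 29% of it, but r falling through 0.5, 0.4, 0.3 and 0.2 explains 0.35²/0.85 = 14%. The benefit would roughly halve.

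Protocol 3.2.a does bound the candidate covariates, and the footnote to Table 2.A mentions five time points, which could mean baseline plus four visits. Neither supplies a selection rule. Open-label care does not let anyone steer baseline balance, and the data coordinating center is independent of the sites. The exposure is only that the model may be chosen with by-arm data in view.

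Remitters are few: 60×0.08 = 4.8 expected in the LCR arm at one visit. At 60 per arm, fitting problems occurred in under 1% of simulated single-visit data sets.

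**Conclusion.** The point holds as a worthwhile improvement with a modest gain, not as an error that threatens the trial. The primary Aim 1A models leave covariate choice to an undefined, data-dependent trigger, and no other section fixes baseline %mBMI or EDE-Q in them.

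For remission, the gain from always adjusting is about 1 to 2 points of power at r = 0.3 and about 1 to 6 at r = 0.5. Larger gains need r = 0.7 for both measures, which is optimistic, and the largest also need a strict cut-off. For continuous %mBMI at one visit the gain is 1.1 to 3.0 points at r = 0.3 and 2.8 to 8.4 at r = 0.5, less or nothing if baseline is already modelled as an outcome. All figures depend on assumed r and cut-offs, and shrink if r declines over follow-up.

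**What to change.** In SAP 2.2, Aim 1A:

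- Delete the imbalance trigger. Name baseline %mBMI and baseline EDE-Q as fixed effects in every Aim 1A model, with an arm-blind rule for a missing baseline EDE-Q, such as the overall mean.
- State which adjusted arm contrast is the main one: the average over the four months, or one month such as month 3, as in Table 2.A.
- Take the test from the model. Beside the conditional odds ratio, report a marginal (standardised) risk difference with a bootstrap CI. With an influence-function SE, the risk difference rejected in 5.7–5.9% of null trials, against 4.8–5.0% for the model's Wald test.
- Say whether baseline is a modelled outcome (as SAP 2.5 implies) or a covariate.

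Two side points. Site has two levels and is the randomization stratum, so enter it as a fixed effect: a two-site variance is estimated as zero in about 68% of trials at ICC 0 and 38% at ICC 0.05 (60/60 split). The arm estimate should change little. For Aim 1B, a log-rank test stratified by site is reasonable, with any covariate-adjusted Cox estimate supportive; no gain was quantified there.

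The cost is SAP wording, with no new data, fixed before remission is compared by arm. The downsides are two more terms with about 18 to 22 expected remitters at one visit (51×0.36 = 18.4; 60×0.36 = 21.6), the missing-EDE-Q rule, and an odds ratio that changes with the covariates, hence the marginal risk difference.

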2.4. Data Management

a. DCC: [name] at UCSF will lead the DCC, which will be autonomous and independent of the clinical sites. It is housed in the UCSF Department of Preventive and Restorative Dental Sciences (PRDS). The department is staffed primarily by statisticians and scientific researchers who conduct data-intensive research, collaborative data collection and analyses from multiple sites. They are equipped with an independent network of sophisticated and reliable computer systems with high-level security for protecting health information. The network is maintained by an in-house computer staff, which manages all aspects of the network, including ongoing maintenance, installation and upgrades of hardware, software and structural components such as cabling and servers. [name] is the lead biostatistician and routinely guides the work of Master-level statisticians, data managers and programmers. **[name]** will continue as faculty biostatistician and DCC leader. She has extensive experience running NIDCR-funded DCCs for clinical trials with more than 8-10 sites nationwide. Thus, UCSF has experience maintaining a distinctly separate but closely coordinated working relationship between clinical sites and data center.

Table 2.A Detectable differences in remission--rates:

ρ^*	LCR	HCR	Mo---3 Diff
1.0	8%	28%	20%
0.8	14%	34%	20%
0.6	16%	34%	18%
0.4	18%	34%	16%
0.2	20%	34%	14%
0.1	22%	34%	12%

Table 2.B. Detectable differences in time to medical stability-rates

ρ^*	LCR	HCR	Difference
1.0	72%	92%	20%
0.8	66%	86%	20%
0.6	66%	84%	18%
0.4	66%	82%	16%
0.2	66%	80%	14%
0.1	66%	78%	12%

*correlation among 5 time points within participant

b. Electronic data capture: Both clinical sites are equipped with the same Research Electronic Data

Capture (Qualtrics) system for databases, data entry forms, online questionnaires and data validation. Data will be automatically exported to STATA or SAS for analysis using The Data Export Utility. The DCC uses advanced features including branching logic for dynamic data entry form generation, file uploading, data importing, and embedded calculated database fields.

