2.5. Retention and Attrition

We expect to retain 85% of our sample through one year of follow-up. This is consistent with other open follow-up studies of AN and feasible given our patients volumes and return rates. We will actively retain participants by providing incentives: movie tickets upon enrollment and a \$50 for every follow-up visit attended. Primary analyses will use intent-to-treat longitudinal models that will include outcomes from randomization through the time of dropout or 12 mo, whichever is longer. Secondary analyses will adjust models for baseline covariates that may be associated with loss to follow-up. We anticipate very few missing outcomes because weight and vital sign (medical stability) measures are SOC in AN care during hospital and at follow-up and the majority of patients hospitalized at our programs return to us for follow-up care. Reasons for refusal to participate will be collected from patients and families who decline enrollment.

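### SAP 2.2 names the time-by-treatment interaction as the Aim 1A effect, but SAP 2.3 powers a level difference in remission rates, so the stated 80% power does not apply to the named effect

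*Combined protocol and SAP*

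**What the plan says.** SAP 2.2 (Outcomes, Aim 1A) fits a generalized linear mixed model that "will compare study arms with respect to achievement and maintenance of clinical remission". Remission is scored yes/no at months 1, 3, 6 and 12. The fixed effects are time, group and their product; the coding of time is not given. One sentence identifies the treatment effect: "The time*treatment group interaction provides mITT effect of HCR compared to LCR on clinical remission over time". The next adds: "The average remission rates and scores and their 95% confidence intervals (CIs) will be estimated from the model". No between-arm test of those averages is named.

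SAP 2.3 says that with 60 per arm "we have 80% power on 2-sided 0.05-level test to detect a 20% difference (8% vs. 28%) if data were cross-sectional", and continues: "Our longitudinal data will allow detection of smaller effects, especially if the correlation among outcomes is low". Table 2.A then lists detectable differences in remission rate by rho. Its column header points to month 3.

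The time points are described in several ways:
- SAP 2.2 lists four visits.
- The Table 2 footnote defines rho as "correlation among 5 time points within participant".
- SAP 2.5 refers to "longitudinal models that will include outcomes from randomization through the time of dropout or 12 mo".
- Protocol 3.2.c has five follow-up visits, but Protocol Table 1 has no EDE-Q at day 10, so remission cannot be scored there.
- Protocol Table 1 also collects EDE-Q and weight at admission and discharge.

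**The concern.** Every visit listed in SAP 2.2 follows the end of the randomized treatment. In a model on those visits, the product term is zero whenever the arms differ by a constant amount. It asks whether the gap widens or narrows. The Aim 1A hypothesis and the sample size concern whether the arms differ in remission.

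The protocol (section 2) says the trial is powered on Aim 1A, so the primary conclusion is at stake. A steady benefit of the planned size would usually be reported as non-significant on the named effect, while the averaged rates from the same model differed significantly. The sign can also mislead. If LCR catches up with HCR, the linear-time interaction is negative for HCR although HCR is never worse. Because averages with intervals are also planned, the conclusion depends on which term is read, and the plan does not settle that before the data are seen.

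**Working it through.** **Inputs.** From SAP 2.3 and Table 2.A: 60 per arm, two-sided 0.05, the rate pairs, rho, and 85% retention. From the Table 2 footnote: m = 5. From SAP 2.2: m = 4. Assumed, because the documents do not give them: timing of dropout (cumulative 0/5/10/15% at months 1/3/6/12) and all visit-by-visit trajectories.

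**Step 1: reproduce the plan's figure.** For a level difference averaged over m visits, the design effect is DE = (1 + (m-1)rho)/m and n_e = 60/DE. With p̄ the mean of the two rates,

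power = Φ{[d√n_e - 1.96√(2p̄(1-p̄))] / √(p1(1-p1) + p2(1-p2))}.

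- rho = 1 (8% v 28%): (0.20×√60 - 1.96×0.5433)/0.5246 = (1.549 - 1.065)/0.5246 = 0.923, so power is 82%. Using the average variance throughout gives 81.4% and 58 per arm.
- rho = 0.4 (18% v 34%), m = 5: DE = 2.6/5 = 0.52 and n_e = 115.4; (1.719 - 1.216)/0.6099 = 0.824, so power is 80%.

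The other rows follow in the same way (table below). Table 2.A is therefore a power table for a time-averaged level difference. The role of rho agrees: low correlation helps an average, whereas interaction power rises with rho.

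**Step 2: four visits and dropout.** With m = 4 and partial data kept, n_e = 60 × Σ w_k·k/(1+(k-1)rho), where 5%, 5%, 5% and 85% of patients have 1, 2, 3 and 4 visits. At rho = 0.1: 0.85×3.077 + 0.05×(2.5 + 1.818 + 1) = 2.881, so n_e = 172.9 and power is 70%.

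**Step 3: simulate the planned model under a steady gap.** Random-intercept logistic model, months 1/3/6/12, staged dropout, likelihood-ratio tests, 800 trials per row. All results are % rejection.

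| rho | LCR v HCR | Formula m=5 | Formula m=4 | m=4, dropout | GLMM average | Interaction, linear time | Interaction, categorical |
|---|---|---|---|---|---|---|---|
| 1.0 | 8 v 28 | 82 | 82 | 82 | – | – | – |
| 0.8 | 14 v 34 | 81 | 80 | 80 | 80.6 | 5.6 | 6.5 |
| 0.6 | 16 v 34 | 79 | 78 | 77 | 81.6 | 6.2 | 5.8 |
| 0.4 | 18 v 34 | 80 | 77 | 76 | 76.2 | 4.4 | 4.6 |
| 0.2 | 20 v 34 | 82 | 78 | 76 | 80.9 | 4.4 | 5.9 |
| 0.1 | 22 v 34 | 79 | 73 | 70 | 68.5 | 5.9 | 4.9 |

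Under the null (26% in both arms, rho 0.4) the average rejects in 5.6% and the interaction in 5.0%. The steady-gap interaction results are therefore just its type I error.

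**Step 4: changing gaps** (assumed trajectories; results at rho 0.4 / 0.6).

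| Trajectory, months 1/3/6/12 | Average | Interaction, linear | Interaction, categorical |
|---|---|---|---|
| Mild widening: LCR 8/10/12/14, HCR 14/22/28/34 | 75.2 / 62.5 | 13.5 / 19.5 | 13.0 / 16.4 |
| Opening from zero: LCR 8 throughout, HCR 8/15/21/28 | 53.4 / 39.9 | 56.2 / 73.9 | 47.8 / 67.6 |
| LCR catch-up: LCR 8/15/21/28, HCR 28 throughout | 49.6 / 42.8 | 73.0 / 86.4 | 64.6 / 81.5 |

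In the catch-up case every significant linear-time interaction was negative for HCR.

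**Step 5: would an earlier time point repair it?** Protocol 2.1 excludes patients in remission, so the admission rate is 0% in both arms.
- Admission added, steady gap, logit scale: interaction 2-4% (rho 0.6 to 0.1).
- Admission added, linear scale, visit categorical, no dropout: 82/72/48/30/19% for rho 0.8/0.6/0.4/0.2/0.1. With linear time: 51/36/18/14/12%.
- Discharge added at an assumed 2-5% in both arms (rho 0.4-0.6), logit scale: 5-8% with linear time and 10-25% categorical, against 72-75% for the four-visit average. On a linear scale: 22-44% and 52-78%.

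The planned site random effect was not simulated.

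**The case against.** The strongest reply is that SAP 2.2 never labels the interaction as the primary test. The model is said to compare arms, includes group as a fixed effect, and will yield average rates with intervals. With categorical time, the sentence could loosely mean the visit-by-visit arm differences, which would suit an aim about achieving and maintaining remission. It stands that the level contrast is available from the planned model. It does not stand that the plan has chosen it: the only term described as giving the HCR-LCR effect is the product term, and no test of the averages is named. The looser reading gives four visit differences and no rule for choosing among them.

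Second, the 5% figure holds only for a constant gap. That is correct. With a gap opening from zero or closing, the interaction matches or beats the average in nearly every comparison in Step 4. But SAP 2.3 states no trajectory, so its 80% still was not calculated for that term.

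Third, a single-visit contrast would be as legitimate as an average. In the opening-gap case, a month-12 comparison of 8% v 28% with 51 per arm has about 76% power. This is a fair alternative. The average is preferred here because it is the quantity that Table 2.A reproduces.

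Fourth, the time-point discrepancies are partly benign. The day-10 visit cannot carry remission, and admission plus four visits makes five. What remains is four against five, and whether admission or discharge enters the model. The month-3 column header is a minor wording point.

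**Conclusion.** The plan is wrong as written and must be fixed. The stated 80% power belongs to a time-averaged level difference over five time points (79-82% across the six rows), not to the interaction that SAP 2.2 names. Under a steady Table 2.A gap the named effect is non-significant in about 95% of trials, while the averaged contrast is significant in roughly 70-80%. This rests on a constant gap, 60 per arm, rho from 0.1 to 0.8 and the assumed dropout timing. Under other trajectories the interaction's power ranged from 13% to 86% in the scenarios tried. The mismatch itself needs no simulation: the two sections describe different contrasts. The percent-mBMI model is outside this point.

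**What to change.** In SAP 2.2, for binary remission, name one primary two-sided 0.05 test: the HCR-LCR contrast averaged over months 1, 3, 6 and 12 from the same mixed model, with visit categorical. Keep the time-by-treatment interaction and the visit-specific differences as secondary. State which time points enter the model, and reconcile SAP 2.2, the Table 2 footnote, SAP 2.5, Protocol 3.2.c and the admission and discharge EDE-Q and weight in Protocol Table 1.

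In SAP 2.3, restate Table 2.A for the visits analysed, using all available data under a stated dropout pattern, and make the column header name the quantity tabulated.

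The cost is SAP wording and a new power table; data and model are unchanged. Restated power falls below 80% in most rows: 70-80% for rho below 1 with staged dropout, and as low as 68% at rho 0.1 if all 15% are lost just after month 1. The average is less sensitive to an effect at one visit. It also has less power than the interaction if the gap opens from zero (40-53% against 48-74%) or closes (43-50% against 65-86%); the secondary analyses cover those cases. Appendix Table 2 (Amendment 1) records that the randomization code was broken for the short-term analysis in July 2019, so the change must be documented as made before 12-month data are analysed by arm.
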